9.1.4 Target/Non-Target Lesions

All measurable lesions, up to a maximum of 2 lesions per organ and 5 lesions in total, should be identified as target lesions to be measured and recorded at baseline. The target lesions should be representative of all involved organs. Target lesions will be selected based on their size (the lesion with the longest diameter) and suitability for accurate repeated measurements. At baseline, a sum of the longest diameters for all target lesions will be calculated and recorded as the baseline tumor burden. The baseline sum will be used as the reference point to determine the objective tumor response of the target lesions.

Measurable lesions other than the target lesions and all sites of non-measurable disease will be identified as non-target lesions and will be recorded at baseline. Non-target lesions will be evaluated at the same assessment time points as target lesions.

9.1.5 Response in Measurable Lesions (RECIST 1.1)

At baseline, the sum of the longest diameters (SumD) of all target lesions (up to 2 lesions per organ, up to 5 lesions total) is measured. At each subsequent tumor assessment, the SumD of the target lesions and of new, measurable lesions (≥10; up to 2 new lesions per

organ, total 5 new lesions) are added together to provide the total measurable tumor burden (TMTB):

TMTB = SumD target lesions + SumD new, measurable lesions

Percentage changes in TMTB per assessment time point describe the size and growth kinetics of both old and new measurable lesions as they appear. At each tumor assessment, the response in target and new measurable lesions is defined based on the change in TMTB.

- Complete Response (CR): Disappearance of all target lesions. Any pathological lymph nodes (whether target or non-target) must have reduction in short axis to <10 mm.
- Partial Response (PR): At least a 30% decrease in the sum of diameters of target lesions, taking as reference the baseline sum diameters.
- Progressive Disease (PD): At least a 20% increase in the sum of diameters of target lesions, taking as reference the smallest sum on study (this includes the baseline sum if that is the smallest on study). In addition to the relative increase of 20%, the sum must also demonstrate an absolute increase of at least 5 mm. (Note: the appearance of one or more new lesions is also considered progression).
- Stable Disease (SD): Neither sufficient shrinkage to qualify for PR nor sufficient increase to qualify for PD, taking as reference the smallest sum diameters while on study.

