9.1.9 Overall Response

Overall response will be determined based on RECIST 1.1 criteria and by irRECIST criteria (Table 6). Overall response according to irRECIST is derived from the responses in measurable lesions (based on TMTB) and the presence of any non-measurable lesions.

Table 6 Tumor Response Evaluation: Comparison of RECIST 1.1 and irRECIST

Criteria	RECIST 1.1	irRECIST
New measurable lesions (≥ 10 mm)	Always represents PD	Incorporated into tumor burden
New non- measurable lesions (< 10 mm)	Always represents PD	Does not define progression but precludes irCR
Non-Target lesions	Changes contribute to defining BOR of CR, PR, SD, and PD	Contribute to defining irCR (complete disappearance required)
CR	Disappearance of all lesions	Disappearance of all lesions
PR	≥ 30% decrease in the sum of the longest diameter of all target lesions compared with baseline, in absence of new lesions or unequivocal progression of non-target lesions	≥ 30% decrease in tumor burden compared with baseline

Criteria	RECIST 1.1	irRECIST
SD	Neither sufficient shrinkage to qualify for PR nor sufficient increase to qualify for PD, taking as reference the smallest sum diameters while on study	Neither a 30% decrease in tumor burden compared with baseline nor a 20% increase compared with nadir can be established
PD	At least 20% increase in sum of diameters of target lesions, taking as reference the smallest sum on study. In addition to the relative increase of 20%, the sum must also demonstrate an absolute increase of at least 5mm. The appearance of one or more new lesions is also considered progression.	At least 20% increase in tumor burden compared with nadir (at any single time point) ^a

irRECIST = immune-related Response Evaluation Criteria in Solid Tumors; BOR = best overall response; CR = complete response; irCR = immune-related complete response; PD = progressive disease; PR = partial response; SD = stable disease;

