9.1.10 Best Overall Response (RECIST 1.1)

The best overall response is the best response recorded from the start of the study treatment until the end of treatment taking into account any requirement for confirmation. The subject's best overall response assignment will depend on the findings of both target and non-target disease and will also take into consideration the appearance of new lesions (Table 7).

Table 7 Best Overall Response (RECIST 1.1)

Target Lesions	Target Lesions Non-Target Lesions		
Baseline (Index) and New Measurable Lesions	Baseline Lesions	Baseline Lesions Unequivocal New Lesions	
CR	CR	No	CR
CR	Non-CR/Non-PD	No	PR
CR	NE	No	PR
PR	Non-PD or NE	No	PR
SD	Non-PD or NE	No	SD
Not all evaluated	Non-PD	No	NE
PD	Any	Yes or No	PD
Any	PD	Yes or No	PD

a Subjects with an initial finding of progressive disease (irPD) before or at the 12-week imaging assessment, but without rapid clinical deterioration, require confirmation of irPD with a second, consecutive scan obtained ≥ 4 weeks from the initiation documentation. Subjects will continue to receive study treatment until irPD is confirmed at this later time point. Best overall response (BOR) will therefore include responses occurring at any time before disease progression and after early progression (i.e., within the first 12 weeks of the study).

Target Lesions	Non-Target Lesions		
Baseline (Index) and New Measurable Lesions Baseline Lesions		Unequivocal New Lesions	Overall Response
Any	Any	Yes	PD

CR = complete response; NE = not evaluable at a particular time point; PR = partial response; SD = stable disease; PD = progressive disease

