14.2 Statistical Analysis Plan

This is a Phase 1 open-label, multi-center clinical trial. Descriptive statistics will be employed to evaluate the safety and tolerance of ADXS11-001. Summary statistics for continuous variables will include mean, standard deviation, median and range. Categorical variables will be presented as frequency counts and percentages; and time-to-event variables will be summarized by Kaplan-Meier medians and survival plots. Data listings will be created to support tables and present data. The safety analysis will be performed on the safety population. The efficacy analysis will be performed on the efficacy population. SAS 9.2 or higher will be used for data analysis.

The data will be tabulated and analyzed with respect to subject enrollment and disposition, demographic, and baseline characteristics.

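### Section 9.1.5 and Table 7 carry irRECIST tumor-burden wording into RECIST 1.1, so an assessor can record PR or SD where the protocol's own RECIST 1.1 rule gives PD

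*Combined protocol and SAP*

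**What the plan says.** Section 9.1.5 (RECIST 1.1) holds two rules.

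- **Burden rule.** The section defines "TMTB = SumD target lesions + SumD new, measurable lesions" and then says "At each tumor assessment, the response in target and new measurable lesions is defined based on the change in TMTB".
- **Target-lesion rule.** The bullets that follow do not use TMTB. PR is "At least a 30% decrease in the sum of diameters of target lesions, taking as reference the baseline sum diameters". PD also refers to the target sum and adds "Note: the appearance of one or more new lesions is also considered progression". The PR bullet has no condition on new lesions.

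Other places that bear on the point:

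- Section 9.1.6 (irRECIST) has nearly the same TMTB text. It lists adding new measurable lesions to the burden among the features that separate irRECIST from RECIST.
- Section 9.1.7 (RECIST 1.1, non-measurable lesions) repeats that a new lesion is progression.
- Table 6 in Section 9.1.9 says of a new measurable lesion under RECIST 1.1: "Always represents PD". Its RECIST 1.1 PR row requires that there be no new lesions.
- Table 7 in Section 9.1.10 (RECIST 1.1) heads its target column "Baseline (Index) and New Measurable Lesions", the same heading as irRECIST Table 8. Its last row gives PD whenever the new-lesion column is Yes.

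**The concern.** The two criteria are reported side by side, and their main difference is how they treat new lesions. Section 9.1.5 applies to RECIST 1.1 the very feature that 9.1.6 says distinguishes irRECIST. Table 7 does not settle the matter. If new measurable lesions belong to the target column, an assessor can count such a lesion in the sum, enter No for new lesions, and read off PR or SD.

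Tumor response and PFS by both criteria are secondary objectives (Section 4.2). The response rate, the stable disease rate, the durations and PFS in Section 14.5.5 all rest on these labels. Two assessors could label the same scan differently, each with a sentence of the protocol in support. If the TMTB rule were applied throughout, the contrast on new measurable lesions set out in Table 6 would disappear.

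**Working it through.** There is no planned figure to reproduce. Section 14.2 says "Descriptive statistics will be employed to evaluate the safety and tolerance of ADXS11-001", Section 14.5.5 makes the efficacy summaries descriptive too, and no power or error rate is stated. The check is to score the same record under each rule.

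**Inputs from the documents.** PR is a fall of at least 30% from baseline. PD is a rise of at least 20% and at least 5 mm from the smallest sum (Section 9.1.5). A new lesion counts as measurable from 10 mm (Table 6). About 15 subjects are to be treated at the expanded dose (Section 14.3).

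**Assumption.** Lesion sizes are illustrative, since the documents give none. In each record this is the first scan after baseline and there is one new measurable lesion.

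**Formula.** TMTB change = (target sum now + new lesion) / baseline sum - 1.

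| Record | Baseline | Targets now | New lesion | TMTB change | On TMTB | Target sum alone | PD note and Table 6 |
|---|---|---|---|---|---|---|---|
| 1 | 100 mm | 45 mm | 20 mm | (45+20)/100 - 1 = -35% | PR | 45/100 - 1 = -55% (PR) | PD |
| 2 | 60 mm | 58 mm | 10 mm | (58+10)/60 - 1 = +13.3% | SD | 58/60 - 1 = -3.3% (SD) | PD |

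The target sum alone gives the same category as TMTB in both records. The move to PD therefore comes from applying the new-lesion rule. The TMTB wording does harm because it invites the assessor to treat the new lesion as already counted, and so to leave that rule unapplied.

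**How easily PR is reached on TMTB.** PR needs target sum now ≤ 0.7 × baseline - new lesion, which is target shrinkage of at least 30% + (new lesion / baseline).

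| Baseline | New 10 mm | New 15 mm | New 20 mm | New 30 mm |
|---|---|---|---|---|
| 100 mm | 40% | 45% | 50% | 60% |
| 50 mm | 50% | 60% | 70% | 90% |

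PR thus needs substantial shrinkage. SD needs much less, as record 2 shows.

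**Effect of one subject on a rate.** 1/15 = 6.7 points, 1/12 = 8.3 points, 1/6 = 16.7 points. Record 1 moves both the response rate and the stable disease rate, because Section 14.5.5 counts CR, PR and SD in the latter. Record 2 moves only the stable disease rate.

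**Effect on PFS.** Under the TMTB reading the progression at that scan is not recorded. The event is then picked up later, at another scan or at death, or it is lost if the subject is censored at discontinuation or completion (Section 14.5.5).

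**The case against.** The best defense is that the documents already give the answer several times. The note in 9.1.5, Section 9.1.7, Table 6 and the last row of Table 7 all make a new lesion PD under RECIST 1.1, and 9.1.6 says that adding new lesions to the burden is an irRECIST feature. This stands as evidence of intent. It does not remove the conflicting sentence, and the Table 7 heading supports that sentence.

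A reader might infer that the protocol requires PR or SD for such a subject, or that using TMTB in place of the target sum is what changes the category. The documents support neither. PR or SD is a possible misreading, and in both records above the target sum gives the same category. For PR, TMTB is in fact the stricter sum, because it adds millimeters.

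A reader might also infer that every such subject shifts the rates and that PFS always moves by at least one 12-week scan interval. That goes too far:

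- Best overall response is the best since the start of treatment (Section 9.1.10), so an equal or better response at an earlier scan leaves the rate unchanged.
- Death is a PFS event at any time, routine scans have a window of one week either side (Section 8.1), and censoring can remove the event altogether.

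The Table 7 header is broken in the extracted text, so whether its new-lesion column is grouped under non-target lesions is an inference. The target column heading is clear.

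Finally, the endpoints are secondary and descriptive, and the recommended dose is chosen on the DLT rate (Section 6). That limits the weight of the point but does not make the text consistent.

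**Conclusion.** The point holds as a defect in a stated scoring rule. Section 9.1.5 and the Table 7 heading contradict the protocol's own RECIST 1.1 rule and leave room to score PR or SD where that rule gives PD.

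The size is conditional. If no equal or better response came at an earlier scan, one affected subject moves the RECIST 1.1 response rate or stable disease rate by about 6.7 points. This takes all of about 15 subjects as the denominator. The shift is larger if fewer complete the cycle that Section 14.5 requires for the efficacy population. Her PFS event at that scan is missed, and so delayed or lost to censoring. How many subjects would be affected cannot be known from the documents. The primary safety objective and the choice of recommended dose do not depend on it. The text should be corrected before any response data are scored or analyzed.

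**What to change.** 1. In Section 9.1.5, delete the TMTB paragraph, formula and sentence, so that RECIST 1.1 uses the baseline target-lesion sum only, with any new lesion as PD.
2. In the 9.1.5 PR bullet, add the condition that no new lesions are present, to match Table 6.
3. In Table 7, head the first column *Target lesions (baseline)* and the new-lesion column *Any new lesion (measurable or not)*.
4. Keep TMTB for irRECIST only (Section 9.1.6 and Table 8). Reconcile the Table 8 row that gives irPD for any new lesion with 9.1.6 and Table 6, where a new lesion does not by itself define irRECIST progression.

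The cost is the wording of one section and two tables. No new data or assessments are needed. Any RECIST 1.1 assessment already scored on a record with a new measurable lesion should be checked against the corrected rule.

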9.1.6 Immune-Related Response in Measurable Lesions (irRECIST)

In addition to evaluation using RECIST 1.1 criteria, an immune response adaptation of RECIST will be applied to this trial. The essential differences between irRECIST and RECIST criteria are as follows:

- New measureable lesions do not necessarily constitute progressive disease and they should be added into the total tumor burden. New non-measurable lesions do not constitute disease progression but will prevent the determination of an irCR.
- Apparent disease progression should be confirmed after 4 weeks in the absence of symptoms consistent with clinical deterioration.

At baseline, the sum of the longest diameters (SumD) of all target lesions (up to 2 lesions per organ, up to total 5 lesions) is measured. At each subsequent tumor assessment (TA), the SumD of the target lesions and of new, measurable lesions (\geq 10 mm [lymph nodes \geq 15 mm in shortest diameter]; up to 2 new lesions per organ, total 5 new lesions) are added together to provide the total measurable tumor burden (TMTB):

TMTB = SumD target lesions + SumD new, measurable lesions

Percentage changes in TMTB per assessment time point describe the size and growth kinetics of both old and new, measurable lesions as they appear. At each tumor assessment, the response in target and new, measurable lesions is defined based on the change in TMTB (after ruling out irPD) as follows:

- Complete Response (irCR): complete disappearance of all target and new, measurable lesions, with the exceptions of lymph nodes which must decrease to <10 mm in short axis
- Partial Response (irPR): decrease in TMTB ≥30% relative to baseline (see below)
- Stable Disease (irSD): not meeting criteria for irCR or irPR, in absence of irPD
- Progressive Disease (irPD): increase in TMTB ≥20% relative to nadir

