9.1.8 Immune-Related Response in Non-Measurable Lesions

At each tumor assessment, the presence of any new, non-measurable lesions is assessed. The presence of such lesions will rule out an overall response of irCR. An increase in the size or number of new, non-measurable lesions does not necessarily imply an overall response of irPD; if these lesions become measurable (≥ 10 mm) at a subsequent tumor assessment, their measurement will at that point start to contribute to the TMTB.

In addition, the response in non-target lesions is defined as follows:

- Complete Response (irCR): complete disappearance of all non-target lesions
- Stable Disease (irSD): non-target lesions are stable
- Progressive Disease (irPD): unequivocal increases in number or size of non-target lesions. To achieve unequivocal progression of non-target lesions, there must be an overall level of substantial worsening of non-target disease that is of a magnitude that the treating physician would feel it is important to change therapy.

NOTE: Equivocal findings of progression of non-target lesions (e.g., small and uncertain new lesions; cystic changes or necrosis in existing lesions) should be considered irSD, and treatment may continue until the next scheduled assessment.

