9.1.11 Immune-Related Best Overall Response (irRECIST)

The immune-related best overall response (irBOR) is the best irRC overall response over the study as a whole, recorded between the date of first dose until the last tumor assessment prior to subsequent therapy (including tumor resection surgery) for the individual subject in the study (Table 8). As with the primary definitions of tumor response, early progression (i.e., irPD occurring prior to Week 12) will not preclude an irBOR of irCR, irPR or irSD resulting from the Week 12 assessment. An assessment of irPD at or after Week 12 will preclude a subsequent irBOR of irCR, irPR or irSD. However, any post-progression clinical activity in subjects with irBOR of irPD may be summarized for exploratory purposes.

Table 8 Immune-Related Best Overall Response (irBOR)

Target Lesions Baseline (Index) and New Measurable Lesions Non-Target I		Lesions ^a	
Total Measurable Tumor Burden	Baseline Lesions	Unequivocal New Lesions	irRC Overall Response
irCR	irCR	No	irCR
irCR	irSD	No	irPR
irPR	irCR or irSD	No	irPR
irSD	irCR or irSD	No	irSD
irPD	Any	Yes or No	irPD
Any	Unequivocal Progression	Yes or No	irPD
Any	Any	Yes	irPD

irCR = immune-related complete response; irPR = immune-related partial response; irSD = immune-related stable disease; irPD = immune-related progressive disease

^a Any increase in the size or number of non-measurable lesions does not necessarily imply an overall response of irPD. If these lesions become measurable (≥10 mm) at a subsequent assessment, their measurement will at that point start to contribute to the total measurable tumor burden. To achieve unequivocal progression of non-target lesions, there must be substantial worsening in non-target disease that is of a magnitude that the Investigator feels it is important to change therapy. Equivocal findings of progression of non-target lesions (e.g., small and uncertain new lesions; cystic changes or necrosis in existing lesions) should be considered irSD, and treatment may continue until the next assessment.

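### Table 8 turns a definite new non-measurable lesion into irPD, although Sections 9.1.6 and 9.1.8 and Table 6 say that such a lesion only rules out irCR

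*Combined protocol and SAP*

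**What the plan says.** Section 4.2 makes tumor response and PFS by both RECIST 1.1 and irRECIST a secondary objective. Section 14.5.5 derives ORR, stable disease rate, two durations and PFS from the response categories.

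The irRECIST rule for new lesions appears in five places:

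- **Section 9.1.6**, among the points that set irRECIST apart. For measurable lesions: "New measureable lesions do not necessarily constitute progressive disease and they should be added into the total tumor burden". For the others: "New non-measurable lesions do not constitute disease progression but will prevent the determination of an irCR".
- **Section 9.1.8**: new non-measurable lesions exclude irCR, and "An increase in the size or number of new, non-measurable lesions does not necessarily imply an overall response of irPD". Once they reach 10 mm they enter the total measurable tumor burden (TMTB).
- **Table 6 (Section 9.1.9)**: new lesions of 10 mm or more go into the burden. For those below 10 mm the entry is "Does not define progression but precludes irCR".
- **Table 8, footnote a**: repeats the Section 9.1.8 statement for non-measurable lesions.
- **Table 8, body (Section 9.1.11)**: has a column "Unequivocal New Lesions". The last row gives irPD when that column is *Yes*, whatever the TMTB and the baseline non-target status. All rows ending in irCR, irPR or irSD require *No*.

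Section 9.1.11 adds that irPD at or after Week 12 shuts out a better irBOR later, while irPD before Week 12 does not.

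**The concern.** Four statements treat a new non-measurable lesion as something that blocks irCR and no more. The table that actually assigns the category treats it as progression, which is the new-lesion rule of Table 7 for RECIST 1.1. Table 8 even conflicts with its own footnote.

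Section 9.1.12 explains why immune-related criteria are wanted: response may follow an initial increase in burden or new lesions. For new non-measurable lesions, Table 8 cannot credit that pattern from Week 12 on. Two analysts with the same scans, one working from Section 9.1.6 and one from Table 8, would report different irRECIST response rates and PFS. The trial is open-label, so a rule chosen after the data are seen would be hard to defend as independent of them.

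**Working it through.** The plan gives no figure to reproduce, so the check compares the rules.

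**1. Enumeration.** Take target or TMTB status (CR, PR, SD, PD), baseline non-target status (CR, stable, PD) and new lesion (none, non-measurable, measurable): 4 × 3 × 3 = 36 combinations. Remove the 3 that pair a TMTB of CR with a new measurable lesion, which cannot occur. That leaves 33; not-evaluable rows are left out. Table 8 can be read in two ways:

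- *Narrow*: its new-lesion column means new non-measurable lesions, because it sits under the non-target heading and new measurable lesions are already in the TMTB column.
- *Broad*: the column means any new lesion.

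| Comparison | Narrow | Broad |
|---|---|---|
| Table 8 differs from the text (9.1.6, 9.1.8, Table 6) | 6 of 33 | 10 of 33 |
| Table 8 differs from Table 7 (RECIST 1.1) | 4 of 33 | 0 of 33 |

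The text rule itself differs from Table 7 in 10 of 33. These are counts of category combinations, not of subjects.

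**2. The six conflicts that stand on either reading.** All involve a new non-measurable lesion with non-target status CR or stable.

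- TMTB CR or PR: 2 × 2 = 4 combinations; text irPR, Table 8 irPD. (For TMTB CR, irPR is inferred: irCR is excluded and the fall exceeds 30%.)
- TMTB SD: 1 × 2 = 2 combinations; text irSD, Table 8 irPD.

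The first four change irRECIST ORR. All six change the stable disease rate and irRECIST PFS.

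**3. Example with assumed sizes.** Baseline sum 60 mm; Week 12 targets 36 mm; one definite new lesion of 7 mm, below the 10 mm limit and so outside TMTB; non-target lesions stable.

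- Change in TMTB = (36 − 60)/60 = −40%.
- Section 9.1.6 and Table 6: irPR.
- Table 8, last row: irPD.
- RECIST 1.1: PD.

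**4. Contrast: a new measurable lesion.** Baseline 60 mm, targets 24 mm, new lesion 12 mm: TMTB = 24 + 12 = 36 mm, again −40%. The text gives irPR. Table 8 gives irPR on the narrow reading and irPD only on the broad one, which uses the same lesion in two columns.

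**5. Finality.** Week 12 is the first scheduled scan after baseline (Section 8.3). Under Section 9.1.11, irPD there fixes irBOR. The Table 6 footnote asks for a confirming scan at least 4 weeks later, but if the new lesion is still present the last row of Table 8 again returns irPD.

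**6. Scale.** With 15 subjects (the approximate RP2D cohort in Section 14.3), one reclassified responder is 1/15 = 6.7 percentage points, two are 13.3 and three 20.0. With 12 in the denominator, one is 1/12 = 8.3.

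**7. RECIST 1.1.** Section 9.1.5 says "the response in target and new measurable lesions is defined based on the change in TMTB", which is irRECIST language. With no new lesion, TMTB equals the target sum; with one, the section's own note makes the result PD. No RECIST 1.1 category changes.

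**The case against.** The best defense of Table 8 is the word unequivocal, together with Section 9.1.8, which assigns irPD to "unequivocal increases in number or size of non-target lesions". A definite new small lesion does raise the number of lesions. This lends the column some support, but does not reconcile the passages. Sections 9.1.6 and Table 6 exempt new non-measurable lesions with no such qualifier. Section 9.1.8 deals with new non-measurable lesions separately, and for non-target progression it asks for substantial overall worsening.

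Other objections limit the point, and they stand:

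- A reader might infer that every subject with a new lesion is misclassified. The layout of Table 8 does not support that: its first column already takes in new measurable lesions through TMTB.
- A reader might infer that irRECIST becomes RECIST 1.1. On the narrow reading new measurable lesions are still handled differently. Confirmation of irPD and the allowance for irPD before Week 12 remain, equivocal new lesions count as irSD, and post-progression activity may be summarized.
- A reader might infer that the TMTB wording in Section 9.1.5 distorts RECIST 1.1 results. Step 7 shows that it does not.
- A reader might take Table 6 to say that non-target lesions matter for irCR alone. It names that role without excluding others, so beside Section 9.1.8 and Table 8 it is incomplete rather than contradictory.
- The denominator of 15 is not fixed. Expansion is optional, and Section 14.5 admits only subjects who complete a cycle to the efficacy population.

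**Conclusion.** The contradiction is real for new non-measurable lesions and does not depend on how the Table 8 column is read. Following the table instead of the text changes irBOR, and with it irRECIST ORR, stable disease rate, durations and PFS. For new measurable lesions the fault is an ambiguous header, not an established conflict.

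The size is about 6.7 points of irRECIST ORR per reclassified responder if 15 subjects are in the denominator, and more if fewer complete a cycle. How many subjects would be affected cannot be derived, and the lesion sizes in the examples are assumptions. These endpoints are secondary and descriptive. DLT assessment, MTD, RP2D and sample size are untouched, and RECIST 1.1 results are reported alongside. The correction should be made, but the trial's main purpose does not hang on it.

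**What to change.** Before response is derived:

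1. Reconcile the last row of Table 8, and the *No* entries in its irCR, irPR and irSD rows, with Sections 9.1.6 and 9.1.8, Table 6 and footnote a, so that a single new-lesion rule yields irBOR and irRECIST PFS.
2. Label the new-lesion column so that new measurable lesions count only through TMTB.
3. Bring the Table 6 non-target row into line with Section 9.1.8 and Table 8 on unequivocal non-target progression.
4. State how the Table 6 footnote (confirmation of irPD found before or at 12 weeks) fits with Section 9.1.11 (irPD at Week 12 is final for irBOR).
5. As editing only, take the TMTB text out of Section 9.1.5 and correct the matching header of Table 7.

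For endpoint derivation the cost is protocol and SAP wording, with no added scans or measurements. irPD also bears on whether a subject continues treatment (Table 6 footnote; Sections 6 and 9.1.12). The sponsor must reconcile the passages for that purpose separately; no stopping rule is proposed here.

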9.1.2 Tumor Imaging and Assessment of Disease

Computed tomography (CT) and magnetic resonance imaging (MRI) will be considered the best currently available and reproducible methods to measure target lesions (as

defined in Section 9.1.4, Definition of Target/Non-target Lesions) selected for response assessment. Conventional CT should be performed with contiguous cuts of 10 mm or less. Spiral CT scan should be performed using a 5 mm contiguous reconstruction algorithm (as a general rule, lesion diameter should be no less than double the slice thickness). Lesions on chest x-rays will be acceptable as measurable lesions when they are clearly defined and surrounded by aerated lung; however, CT is preferable. Ultrasound is not an acceptable method to measure disease.

Assessment of disease will be done using both RECIST 1.1 criteria and irRECIST criteria. All subjects who have completed one 12-week cycle of ADXS11-001 treatment will be considered evaluable for response.

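### The irRECIST progression rule has no 5 mm minimum, so in subjects with a nadir sum below 25 mm a small sustained rise is irPD while RECIST 1.1 still gives PR or SD.

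*Combined protocol and SAP*

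**What the plan says.** For target lesions under RECIST 1.1, section 9.1.5 sets two conditions for progression. The first is relative: "At least a 20% increase in the sum of diameters of target lesions, taking as reference the smallest sum on study". The second is absolute: "In addition to the relative increase of 20%, the sum must also demonstrate an absolute increase of at least 5 mm". The RECIST 1.1 column of Table 6 (section 9.1.9) repeats both.

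For irRECIST, section 9.1.6 has the relative condition only: "Progressive Disease (irPD): increase in TMTB ≥20% relative to nadir". The irRECIST column of Table 6 agrees, and nothing elsewhere in the protocol applies a minimum in millimetres to irPD. Under 9.1.6, irPD is excluded before irCR, irPR or irSD is assigned, so irPD takes precedence over irPR.

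Section 9.1.6 introduces its contrast with the words "The essential differences between irRECIST and RECIST criteria are as follows" and lists two items: how new lesions are handled, and confirmation of apparent progression after 4 weeks when there is no clinical deterioration. The missing 5 mm condition is not on that list. Footnote a to Table 6 requires a confirmatory scan at least 4 weeks later, but only for irPD found up to and including the 12-week scan. Section 9.1.12 also calls for a repeat assessment at least 4 weeks after radiological progression. None of these passages sets a size minimum.

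Section 4.2 makes tumor response and PFS under both criteria a secondary objective. In section 14.5.5, PFS and duration of response end at progression or death.

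**The concern.** The protocol treats a rise of less than 5 mm as too small to count as progression under one criterion and as sufficient under the other, although both use the same lesions and the same scans. Both differences listed in 9.1.6 make irPD harder to reach. The unlisted one makes it easier to reach when the tumor sum is small.

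The subjects exposed are those with a small nadir: deep responders, and subjects who enter with one small target lesion (9.1.3 accepts 10 mm on spiral CT or MRI). For them, PFS and duration of response by irRECIST can end while RECIST 1.1 still records PR or SD. Under 9.1.11, irPD at or after Week 12 also rules out a later irCR, irPR or irSD as best response, so a low-burden subject with no earlier response can be counted as irPD rather than irSD. With about 15 subjects planned at one dose level (14.3), a few such calls could move a Kaplan-Meier median.

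**Working it through.** **Inputs.** RECIST 1.1 PD: at least +20% from the smallest sum and at least +5 mm (9.1.5). RECIST 1.1 PR: "At least a 30% decrease in the sum of diameters of target lesions, taking as reference the baseline sum diameters" (9.1.5). irPD: at least +20% in total measurable tumor burden (TMTB) from nadir, tested first (9.1.6). irPR: at least 30% below baseline (9.1.6). The protocol gives no lesion data, so the sums below are illustrative. They assume no new lesions and stable non-target disease, so that TMTB equals the target sum.

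**Where the rules part.** The 5 mm condition matters only when 0.20 × nadir < 5 mm, that is, nadir < 5 / 0.20 = 25 mm. A rise of 2 mm is enough for irPD when 0.20 × nadir ≤ 2 mm, that is, nadir ≤ 10 mm.

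**Cases (mm).**

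| Baseline | Nadir | Current | Rise | From nadir | From baseline | RECIST 1.1 | irRECIST as written | irRECIST with 5 mm floor |
|---|---|---|---|---|---|---|---|---|
| 40 | 8 | 10 | 2 | +25% | −75% | PR | irPD | irPR |
| 50 | 10 | 12 | 2 | +20% | −76% | PR | irPD | irPR |
| 50 | 11 | 13 | 2 | +18.2% | −74% | PR | irPR | irPR |
| 100 | 20 | 24 | 4 | +20% | −76% | PR | irPD | irPR |
| 10 | 10 | 12 | 2 | +20% | +20% | SD | irPD | irSD |
| 50 | 10 | 15 | 5 | +50% | −70% | PD | irPD | irPD |
| 100 | 25 | 30 | 5 | +20% | −70% | PD | irPD | irPD |

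First row: (10 − 8)/8 = +25%; the rise of 2 mm is below 5 mm, so it is not RECIST PD; 10 ≤ 0.70 × 40 = 28, so RECIST stays PR. At nadir 10 mm and current 12 mm, RECIST remains PR only if baseline is at least 12/0.70 = 17.1 mm; otherwise it is SD.

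**Does confirmation remove the discordance?** The 9.1.6 repeat scan has no size minimum, so a sum that stays at 10 mm is still 25% above a nadir of 8 mm. Footnote a covers irPD up to the 12-week scan. Imaging is at Week 12 and then every 12 weeks (8.3), so a rise from a nadir reached at Week 12 first appears on a scheduled scan at about Week 24, outside the footnote. The fifth row, if seen at Week 12, does fall under the footnote and becomes confirmed irPD only if the rise is still present on the second scan.

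**The case against.** The strongest defense is that nothing is hidden or ambiguous. Table 6 sets the two progression rules side by side, 9.1.6 agrees with it, and a list of essential differences need not be complete; Table 6 also shows a difference in non-target handling that the list omits. An analyst can apply both rules as written. This stands: the omission is open in the table, though unlisted and unexplained in 9.1.6.

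Confirmation is the second defense. A reader might infer that one noisy measurement is enough for irPD. The documents do not support that: 9.1.6, footnote a and 9.1.12 all call for a repeat assessment, and random error on one scan is less likely to recur on a second. What survives is the small rise that persists.

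A reader might also take the imaging instruction, "Spiral CT scan should be performed using a 5 mm contiguous reconstruction algorithm", as evidence that changes under 5 mm are measurement error. That is a slice interval, not the error of a diameter, and the documents give no error figure. The sounder argument is that 9.1.5 itself adopts 5 mm as the least increase that counts.

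It would likewise go too far to say that irRECIST must be the more permissive criterion in every case, since no section says so. Nor is every subject with a nadir below 25 mm misclassified: discordance also needs a rise of at least 20% but under 5 mm. Finally, disease progression is a discontinuation criterion (section 6), so changing irPD could affect treatment; that limits what a statistical comment may propose.

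**Conclusion.** The concern holds in a limited form. As written, irPD and RECIST 1.1 PD differ in their absolute condition without explanation. For a nadir sum below 25 mm, a sustained rise of at least 20% but under 5 mm gives irPD alongside RECIST 1.1 PR or SD. The consequence is possible early ending of PFS and duration of response by irRECIST, and an irBOR of irPD in low-burden subjects with no earlier response. An irPR already recorded is not lost, because 9.1.11 blocks only a later one.

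The size of the effect on the summaries is unknown: the documents give no lesion sizes from which to judge how many subjects will have a nadir below 25 mm. The endpoints are secondary and descriptive, and no test, error rate or sample size depends on them. The classification results assume no new lesions and no non-target progression. It is worth correcting because the remedy is small, not because the primary safety objective is at risk.

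**What to change.** For deriving the irRECIST endpoints (PFS, duration of response and irBOR), define irPD on size in 9.1.6 and Table 6 as an increase in TMTB of at least 20% from nadir together with an absolute increase of at least 5 mm, matching 9.1.5. If the difference is intended, add it to the list in 9.1.6 with the reason.

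The cost is one clause in each place and one line in the endpoint derivation; no extra scans are needed. The drawback is that irPD may be dated one scan later, about 12 weeks on the protocol schedule, when tumor burden is very small. Results for a nadir of 25 mm or more do not change. A new measurable lesion adds at least 10 mm to TMTB by definition (9.1.6), so the floor alone would not mask one unless target lesions shrank at the same time.

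Section 6, footnote a to Table 6 and section 9.1.12 link progression or its confirmation to continuing treatment. Those passages must be reconciled with the endpoint definition; this comment proposes no rule for them.
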